### **6.14. Day 90: Visit 4 – Patient Questionnaire Assessment**

Participants will complete questionnaires on Day 90 (+7 days). The study staff will contact participants on Day 92 and after if the questionnaires have not yet been completed. When all questionnaires are completed, the study staff will call or text the participants to confirm that their involvement in the study is complete and to reiterate the instructions on returning the study device.

Questionnaires to be completed:

Health assessments

1. Psychometric Instruments:
  - a. Pittsburgh Sleep Quality Index (PSQI)
  - b. PCL-5
  - c. Insomnia Severity index (ISI)
  - d. (PHQ-9) (Score of 1 or more on the suicide ideation item [question #9] to trigger a risk assessment by the PI, and if necessary, a licensed Behavioral Health Provider.)
  - e. Epworth Sleepiness Scale ESS
  - f. Trauma Related Nightmare Scale (TRNS)

- g. VR-12 Quality of Life (VR-12)
- h. NW Likert Scale for Sleep Quality (NW Likert)
- i. Columbia-Suicidality Severity Rating Scale, Since Last Contact version (C-SSRS)
  - i. Study Staff will immediately contact the PI, and if necessary, a healthcare provider that has been trained to perform a suicide assessment if there is any risk of suicide.

Subjects will be allowed to keep the device at the end of the study, but will be given a \$100 reimbursement if they return it. The device can only be used for NightWare. No other applications are enabled on the device.

### **6.15. Reimbursement Plan**

Subjects will receive \$50 for enrolling and completing study-related surveys at their baseline visit.

At each two-week interval during the Study (Day 15, 30, 45, 60, 75, & 90) study participants will receive \$25 for continuing to participate in the study.

**Study participants will also receive an additional \$25 every two weeks (Day 15, 30, 45, 60, 75, & 90) for wearing the device for  $\geq 70\%$  or 10 of the 15 nights in a two-week period.**

Subjects will also receive \$100 upon returning the device and completing study-related surveys.

In total, participants will receive between \$200-\$450 for participating in the Study, which averages up to \$5/day.

Study participants will also be reimbursed for any travel expenses if required.

Compensation Table

Study Day	Base Amount	Incentive Amount	Condition of incentive Amount
1	\$50		
15	\$25	\$25	Study device use in 10 of last 15 days
30	\$25	\$25	
45	\$25	\$25	
60	\$25	\$25	
75	\$25	\$25	
90	\$25	\$25	
Return of study device		\$100	
TOTAL	\$200	\$250	

## 7. Statistical Considerations

### 7.1. Randomization Procedure

The study will use stratified randomization based on study site and whether the participant has a baseline PSQI score equal to or less than 15 versus scores that are equal to 16 or more. This will result in four study strata (groups). See Table #2, below.

**Table #2: Assigned ID numbers for different strata-schema**

NW RCT Assigned ID's	Study Protocol #	Site Number	1 st ID for stratum (low/high PSQI score)	Last ID for stratum	Final ID assigned numbers by stratum
Minneapolis (Mpls) Low PSQI	2	1	001	499	21001-21499
Mpls High PSQI	2	1	500	999	21500-21999
Tampa Low PSQI	2	2	001	499	22001-22499
Tampa High PSQI	2	2	500	999	22500-22999
Walter Reed Low PSQI	2	3	001	499	23001-23499
Walter Reed High PSQI	2	3	500	999	23500-23999
Cleveland Low PSQI	2	4	001	499	24001-24499
Cleveland High PSQI	2	4	500	999	24500-24999
Low PSQI	2	n	001	499	2n001-2n499
High PSQI	2	n	500	999	2n500-2n999

As explained below, throughout the study the Active and Sham Systems will be well balanced in the number of participants from each study stratum. The rationale for imposing balance (equal numbers of participants in each stratum as delineated in table #2, above) based on baseline PSQI score, is that participants with a higher baseline PSQI will have a greater potential for PSQI-score reduction during follow-up, while participants that begin the study with lower scores, will have a correspondingly lower potential for PSQI-score reduction. If these strata were NOT imposed there is a real risk that a higher proportion of participants with LOW starting PSQI-scores would be given the Active System and the HIGH starting PSQI-scores would receive the Sham System. Upon analysis of the strata in this example, any effect that was due to having the Active System would be severely blunted. This would make it seem that the NW System is not as effective as it really is. If, conversely, the Active System was assigned to more baseline HIGH PSQI-scorers, the effect of the NW System could show a much-greater effect than there really is. As explained in the journal JAMA:

**The permuted block technique randomizes patients between groups within a set of study participants, called a block. Treatment assignments within blocks are determined so that they are random in order but that the desired allocation proportions are achieved exactly within each block. In a 2-group trial with equal allocation and a block size of 6, 3 patients in each block would be assigned to the control and 3 to the treatment and the ordering of those 6 assignments would be random. For example, with treatment labels A and B, possible blocks might be: ABBABA, BABBA, and AABABB. As each block is filled, the trial is guaranteed to have the desired allocation to each group.**

Participant ID's will be linked to a randomization schedule to be accessed by the unblinded NightWare programmers (who keep the randomization results secret) so that each participant's NW System may be remotely programmed accordingly as either Active or Sham. This remote programming will occur before the subject arrives home with the study device.

The randomization schedule for each of the four study strata will be generated randomly using permuted blocks (as described above) of size two, four, or six. When, for example, a block size of two is used, one participant will be assigned Active and the other will be assigned Sham; for a block size of four, two will be assigned Active and two will be assigned Sham; and for a block size of six, three will be assigned Active and the other three will be assigned Sham. The assignment order within the block will be randomly chosen with equal probability. For example, the assignment order for a block size of two may be Active, then Sham or Sham, then Active; whereas for a block of four the assignment order is realized in six possible ways, and for a block of six the assignment order is realized in twenty possible ways. Due to the many possible randomization schemes possible it will be difficult to predict the next arm assignment, even for someone who is unblinded to the previous assignments and strata information. After each block of participants has been enrolled in a particular study stratum, the two arms will necessarily have the same number of participants from that study stratum. To generate the randomization schedule for each stratum, a string of block sizes, along with their assignment order, will be randomly selected using the software statistical package R v 3.5.1 and subsequently imported into the randomization document to be accessed by the unblinded NightWare programmers as needed.

## 7.2. Statistical Hypothesis Testing

The primary hypothesis is that NW will improve sleep quality as measured by the Pittsburgh Sleep Quality index (PSQI) relative to sham. On average, compared to the sham, NW will provide a greater reduction in PSQI score measured on day 30 relative to baseline on day 0

Let  $Y_{ij}$  denote the PSQI score for the  $i$ -th participant at their  $j$ -th assessment,  $j=0,1,2$ , where  $j=0$  denotes baseline, and  $i=1,\dots,n$ . Let  $D_i = Y_{i0} - Y_{i1}/2$ , i.e., the difference between the  $i$ -th participant's PSQI score at baseline ( $Y_{i0}$ ) and their average PSQI score across the post-treatment initiation assessment ( $Y_{i1}$ ). The trial will test the hypotheses

$$H_0: \mu_{\text{Active}} \leq \mu_{\text{Sham}} \text{ versus } H_A: \mu_{\text{Active}} > \mu_{\text{Sham}},$$

where  $\mu_{\text{Active}}$  and  $\mu_{\text{Sham}}$  respectively reflect the average difference with NW and sham.

We will evaluate the statistical hypotheses using an equal-variances, two sample t-test. If the equal variance assumption is untenable, we instead will use an unequal-variances, two sample t-test, i.e., Welch's t-test. We will reject the null hypothesis ( $H_0$ ) that change in PSQI from baseline to day 30 resulting from the active NW system is no better than sham when the two-sided p-value is less than or

equal to 0.05 and the direction of the difference favors NW over sham. In this way, the proposed test controls the one-sided type I error rate at 2.5%.

Data will be presented as mean(standard deviation) or median (interquartile range), as appropriate for continuous variables. Categorical variables will be presented as frequency (percentage). Continuous data will be assessed for normality, and transformed as appropriate (e.g. log transformation, square root transformation, etc.). Patient demographics and characteristics will be listed and compared.

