Objectives:	
Primary Objectives:
 
 
● Demonstrate that the Active System improves sleep quality as assessed by the Pittsburgh Sleep Quality Index (PSQI) in participants with PTSD
 
● Demonstrate that improvement in sleep quality is greater for the Active System than the Sham System
 
● Demonstrate that the Active System does not lead to worsening of daytime sleepiness as assessed by the Epworth Sleepiness Scale (ESS)
 
● Demonstrate that there is not an increase in suicide risk as assessed by the Columbia-Suicide Severity Rating Scale (C-SSRS)
 
 
Secondary Objectives:
 
 
● Evaluate changes in the following measures between Day 0 (baseline) and Day 30: 
 
- PTSD severity [PTSD Checklist (PCL-5)]
 
- Sleep quality [PSQI Addendum for PTSD (PSQI-A)]
 
- Subjective sleep quality [NW Likert Scale for Sleep Quality]
 
- Quality of life [Functional Outcomes of Sleep Questionnaire (FOSQ-10) and Veterans Rand 12 Quality of Life instrument (VR-12)]
 
- Nightmare severity/frequency [TRNS]
 
- Depression symptoms [Patient Health Questionnaire-9 (PHQ-9)]
 
 
 

	- Insomnia Severity Index (ISI)
Outcomes:	
Primary Efficacy Outcomes:
 
 
● Difference between PSQI score at baseline (Day 0) and average PSQI score at the post-treatment assessment (Day 30) [i.e., PSQI change] in the Active System.
 
● Difference in average PSQI change scores between Active System and Sham System conditions.
 
 
Primary Safety Outcomes:
 
 
● No significant increase in ESS between baseline (Day 0) and Day 30 in the Active System.
 
● No increase in C-SSRS severity score between Day 0 and Day 30 in the Active System.
 
 
Observational Outcomes:
 
 
● Improvement in sleep quality, nightmare frequency/intensity, quality of life, PTSD severity, and depression symptoms between Day 0 and Day 30 in the Active System.
 
● Greater improvement in sleep quality, nightmare frequency/intensity, quality of life, PTSD severity, and depression symptoms in the Active System relative to the Sham System.
 

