## **6.10. Day 14: Patient Questionnaire Assessment**

Participants will complete questionnaires on Day 14 (+7 days). Study coordinator will contact participants on Day 16 if the questionnaires have not yet been completed. Questionnaires to be completed:

- a. Administer the PCL-5.
- b. Administer the PHQ-9
- c. Pittsburgh Sleep Quality Index (PSQI)

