### 7.3. Sample Size Determination

A total of 240 veterans and active-duty service members will be enrolled (consented) into the study so that even with attrition of up to 50% of study subjects, we can ensure that the study is completed by a MINIMUM of  $n = 120$  participants (60 in each arm) to reach 90% power for rejecting the null hypothesis under the targeted benefit of  $\delta = \mu_{\text{Active}} - \mu_{\text{Sham}} = 3$  points with an equal standard deviation of  $\sigma = 5$  points in each of the two arms. Figure 1 (see below) depicts the power of the trial as a function of the true standardized reduction ( $\delta/\sigma$ ) in the population assuming we enroll and **retain** a MINIMUM of 60 participants in each arm of the proposed trial. If we get more than 60 participants (i.e. less than a 50% attrition rate) this will just make the study results even more powerful.

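### The formula for the primary analysis variable subtracts half of one follow-up PSQI score and leaves its visit unlabelled, so it contradicts the Day 0 to Day 30 change that the protocol states in words

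*Protocol*

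**What the plan says.** Protocol section 7.2 states the primary hypothesis in words as a "greater reduction in PSQI score measured on day 30 relative to baseline on day 0", and its rejection rule also refers to the change from baseline to Day 30. The synopsis (1.1) and the objectives table (section 3) define the efficacy outcome by the same two days, without halving. The between-arm outcome in the synopsis is "Difference in average PSQI change scores between Active System and Sham System conditions".

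The algebra in section 7.2 differs. Assessments are indexed j = 0, 1, 2, "where $j=0$ denotes baseline", and j = 1 and j = 2 get no label. The variable is then defined: "Let $D_i = Y_{i0} - Y_{i1}/2". The gloss on it is "the difference between the $i$ -th participant's PSQI score at baseline ( $Y_{i0}$ ) and their average PSQI score across the post-treatment initiation assessment", which speaks of an average but names one assessment, Y_i1. The means in the null and alternative hypotheses are the arm means of this difference, and section 7.3 powers the trial on them, with a "targeted benefit of $\delta = \mu_{\text{Active}} - \mu_{\text{Sham}} = 3$ points".

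In the randomised phase, PSQI is collected at Day 0, Day 14 and Day 30. The Day 14 list in section 6.10 includes "c. Pittsburgh Sleep Quality Index (PSQI)". The SAP contains no primary efficacy definition; it says only that the safety hypotheses are tested similarly to the primary efficacy hypothesis.

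**The concern.** The printed formula is the only algebraic definition of the primary variable in either document, and it is not a change score: one follow-up score is divided by two before it is subtracted. A divisor of two would make sense for the mean of two follow-up scores, but the formula contains only one.

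The visit is also unclear. If j = 0, 1, 2 follows the PSQI schedule, Y_i1 is Day 14 and the Day 30 score does not enter D at all. If Y_i1 is Day 30, the right score is used but halved.

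At stake is whether the primary result can be computed in one way only. An analyst who codes the formula, one who follows the prose, and one who restores a mean of two follow-up scores would get three different primary estimates. Choosing among them after seeing data would be a post hoc choice of endpoint. The interim analyses in section 7.4 use the same primary endpoint and inherit the ambiguity.

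**Working it through.** **Inputs.** From section 7.2: D_i = Y_i0 − Y_i1/2 and a two-sided 0.05 two-sample t-test. From section 7.3: δ = 3, σ = 5 and 60 completers per arm for 90% power. Assumed, because the documents do not give them: the SDs of PSQI at baseline (s0) and follow-up (s1), and their correlation ρ.

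**1. The plan's own figure.** For the plain change score, the standardised effect is 3/5 = 0.6. The noncentrality is 3 / (5 × √(2/60)) = 3.29 on 118 degrees of freedom, and the noncentral t gives power of 90.3%. The normal approximation gives 90.8% and needs 59 per arm. A simulated three-look O'Brien-Fleming design (final critical value 2.004) gives 90.4%. The stated 90% is reproduced.

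**2. Effect on the estimate.** Randomisation makes the expected baselines equal, so

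- E[D, Active] − E[D, Sham] = −½ × (E[Y1, Active] − E[Y1, Sham]).
- A 3-point lower follow-up PSQI under Active gives ½ × 3 = 1.5 on D.
- Conversely, δ = 3 on D needs a 2 × 3 = 6-point PSQI difference.

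The halving does not depend on the variances. It applies to whichever follow-up score Y_i1 is. If that is Day 14, a 3-point benefit at Day 30 shows as 1.5 only if the full 3 points are already present at Day 14.

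**3. Effect on power.** Var(D) = s0² + s1²/4 − ρ·s0·s1. The SD of 5 is attached to the plain change, so s0² + s1² − 2ρ·s0·s1 = 25. Power is for 1.5 points at 60 per arm (noncentral t):

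| Assumed baseline SD | ρ | s1 | SD of D | Power |
|---|---|---|---|---|
| Equal to s1 | 0.3 | 4.23 | 4.12 | 51% |
| Equal to s1 | 0.5 | 5.00 | 4.33 | 47% |
| Equal to s1 | 0.7 | 6.45 | 4.79 | 40% |
| 3.5 | 0.3 | 4.77 | 3.60 | 62% |
| 3.5 | 0.7 | 6.78 | 2.67 | 86% |
| 2.5 | 0.3 | 5.14 | 3.00 | 78% |
| 2.5 | 0.7 | 6.42 | 2.31 | 94% |

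The SD of D changes along with its mean, so the loss of power is not a fixed amount. It can vanish when the baseline SD is small and the correlation high.

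**4. Type I error.** If the arms have the same distribution of scores, they have the same distribution of D. Halving therefore does not inflate the between-arm type I error.

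**The case against.** The strongest defence is that the endpoint is clear in words. Section 7.2 gives the Day 0 to Day 30 change in its hypothesis and again in its rejection rule, the synopsis and objectives table agree, and section 7.3 justifies 3 points as an ordinary PSQI reduction. A sensible analyst would take the divisor for a drafting remnant and follow the prose. That is the likely origin, and the numerical consequences do depend on the formula being coded as printed. It does not remove the contradiction: the hypotheses and δ are written in terms of this D, and no other text overrides it.

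A reader might infer three stronger points that the documents do not support:

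- **That Y_i1 is the Day 14 score.** This comes from joining the index to the visit schedule; section 7.2 labels only baseline. PSQI is also collected at Days 60 and 90, so the index does not simply list the PSQI visits. The synopsis attaches the post-treatment assessment to Day 30, which points the other way.
- **That an unchanged Active participant would show at least 5 points of improvement.** With entry at PSQI 10 or more, D would indeed be at least 10/2 = 5 under no change. But section 7.2 uses D for the between-arm hypotheses. Sections 1.1 and 3 define the Active-arm change separately, without halving, and nothing says D is used for it.
- **That the trial loses about half its power.** That needs equal visit SDs, which the documents do not state. The entry cut on PSQI makes a narrower baseline SD plausible.

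**Conclusion.** The formula is wrong as written and must be corrected before unblinding. It halves one follow-up score, does not identify the visit, and under either reading fails to give the Day 0 to Day 30 change stated elsewhere.

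The firm part of the size is algebraic: with baselines equal in expectation, the between-arm difference in the follow-up score used is halved. The 3-point target and its clinical rationale in section 7.3 then no longer match the tested variable. The uncertain part is power: about 40% to 94% at 60 per arm for the printed variable, with the plain change held at SD 5 and the visit SDs and correlations assumed. Nothing here questions the type I error of the between-arm test or the sample size for the intended endpoint.

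**What to change.** In section 7.2:

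- Define D_i as Y_i0 minus the Day 30 PSQI score, without the divisor.
- Label each j with its study day.
- Remove the wording that describes the individual follow-up score as an average across assessments.

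Copy the definition into the SAP.

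If the sponsor meant the mean of Day 14 and Day 30, the second term should be written as (Y_i1 + Y_i2)/2. The synopsis, the objectives table, the hypothesis text in 7.2 and the sample size basis in 7.3 should then be aligned with it.

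The cost is one formula, the visit labels and one sentence in the protocol, plus one line in the SAP. The Day 30 PSQI is already collected. With the Day 30 change, 60 completers per arm, δ = 3 and SD = 5 give the stated 90% power, so the sample size does not change.

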#### Continuous

variables will be analyzed by category, intervention vs control, by two-sided t-test or Mann-U Whitney, as appropriate. Categorical variables will be compared by Chi-Square test or Fisher's Exact test as appropriate. The change in PSQI score from baseline to day 30 will be tested via repeated measures tests as determined appropriate by a trial statistician.

[figure not shown]
Time-to-event analyses will be conducted to determine time to a reduction of PSQI over the longevity of the study (baseline, visit 2, day 30, day 60, day 90). These analyses may be Kaplan Meier survival curves to determine the time to the median population attaining the 3 point decrease. If appropriate,

univariate cox regression models will be used to determine the hazard ratios of PSQI scores. Additionally multivariable, adjusted, models will be evaluated. All analyses will be conducted at  $\alpha = 0.05$  to alleviate type II errors.

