#### **7.6. Secondary/Exploratory Analyses**

Secondary and Exploratory analyses will be carried out with appropriate regression modeling techniques and hypothesis tests. In particular, we will use longitudinal data analysis methods, such as generalized estimating equations and generalized linear mixed models, to assess temporal variation in the longitudinal outcome measures, and we will carry out two sample t-tests of the secondary hypotheses.

At the conclusion of the trial, the data will be assessed as both intention to treat (ITT) and per protocol. The effect sizes at the conclusion of the analyses will be compared using standard techniques. If the effect size of the per protocol analysis is greater than 10%, data will be reported as intention to treat to decrease probability of type I errors. Both analyses will follow the outline below:

Secondary outcomes, data will be presented as mean(standard deviation) or median (interquartile range), as appropriate for continuous variables. Categorical variables will be presented as frequency

(percentage). Continuous data will be assessed for normality, and transformed as appropriate (e.g. log transformation, square root transformation, etc.). Patient demographics and characteristics will be listed and compared. Continuous variables will be analyzed by category, intervention vs control, by two-sided t-test or Mann-U Whitney, as appropriate. Categorical variables will be compared by Chi-Square test or Fisher's Exact test as appropriate. Longitudinal data will be analyzed by repeated measures tests as appropriate for the variables.

Repeated measure ANOVA will be used to determine the difference in responses at the time points between groups for all survey types and questions, as appropriate. If determined inappropriate Poisson regression models will be used to determine the univariate, univariable, effect size.

Upon secondary outcomes analysis, multivariable, adjusted, models will be used to determine controlled effect sizes. Each variable with a p-value of 0.25 or less in standard distribution test will be included in the model. Backward stepwise regression modeling may be used to best fit the model.

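### The primary PSQI t-test leaves out both randomisation factors, and section 7.2 assigns a second, open-ended test to the same Day 30 change

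*Protocol*

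**What the plan says.** Protocol section 7.1: "The study will use stratified randomization based on study site and whether the participant has a baseline PSQI score" of 15 or less, or 16 or more. The stated reason is that "participants with a higher baseline PSQI will have a greater potential for PSQI-score reduction during follow-up". The section counts four strata, while Table #2 lists four named sites at two PSQI levels each, plus a placeholder row pair for further sites.

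Protocol section 7.2, opening part: "We will evaluate the statistical hypotheses using an equal-variances, two sample t-test", replaced by Welch's test if equal variances cannot be assumed. H0 is rejected at a two-sided p of 0.05 or less in favour of the device, which the section equates with a one-sided error rate of 2.5%. No covariate appears.

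Protocol section 7.2, later part: a general rule for continuous variables allows transformation and a t-test or Mann-Whitney test. The Day 0 to Day 30 PSQI change is then named specifically and "will be tested via repeated measures tests as determined appropriate by a trial statistician". Multivariable adjusted models are mentioned without covariates or role.

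Protocol section 7.6, repeated in the SAP, for secondary outcomes: "Each variable with a p-value of 0.25 or less in standard distribution test will be included in the model", with backward stepwise selection as an option.

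The SAP does not set out the primary efficacy analysis. It says only that the safety hypotheses are tested in a similar way to it.

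**The concern.** There are two separate issues.

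**Efficiency.** The design treats baseline PSQI as prognostic, and the analysis does not use it. Stratifying at 15/16 leaves baseline variation within each stratum. Block balance also applies to randomised participants, whereas section 7.3 allows up to 50% attrition and the SAP analyses those who complete. A model with continuous baseline PSQI uses the remaining information and corrects chance imbalance among completers. A raw change score does so only if Day 30 PSQI rises one-for-one with baseline.

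**Pre-specification.** One part of section 7.2 ties rejection of H0 to a t-test. Another says the same change is tested by a method still to be chosen. If that choice is made with data in hand, the 2.5% one-sided rate no longer holds.

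For the secondary scales, covariates picked by p-value depend on the data, and ordinary standard errors ignore that selection.

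**Working it through.** **Inputs from the protocol.** Difference 3 points, SD of change 5 per arm, 60 completers per arm, two-sided 0.05, 90% power, 1:1 allocation (sections 7.2, 7.3 and 4.1); PSQI of 10 or more at entry (section 5.1). I read the endpoint as Day 0 minus Day 30, as the text states. The printed formula for D_i halves the follow-up score and needs separate reconciliation.

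**Inputs not in the documents.** Baseline SD (s0), Day 30 SD (s1) and their correlation (ρ). All values below are assumptions.

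**Step 1: the plan's figure.** n per arm = 2(1.96 + 1.2816)² × 5²/3² = 58.4, so 59. Power at 60 per arm = Φ(3/(5√(2/60)) − 1.96) = Φ(1.326) = 90.8%, or 90.3% by noncentral t. Simulated power with three O'Brien-Fleming looks is 90.4%. The planned sample size reproduces without adjustment.

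**Step 2: what adjustment removes.** With b = ρ·s1/s0, the slope of Day 30 on baseline, the fraction of change-score variance removed is (1 − b)²·s0²/25. With equal SDs this becomes (1 − ρ)/2. With the change SD fixed at 5, s1 = ρ·s0 + √(ρ²s0² − s0² + 25). Example: s0 = 4 and ρ = 0.3 give s1 = 4.431, b = 0.3323, and 0.6677² × 16/25 = 0.285.

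Each cell gives variance removed, n per arm for 90% power, and power at 60 per arm (normal approximation; unadjusted values are 59 and 91%):

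| Baseline SD | ρ = 0.3 | ρ = 0.5 | ρ = 0.7 |
|---|---|---|---|
| Equal to Day 30 SD | 35%, 38, 98% | 25%, 44, 97% | 15%, 50, 95% |
| 4 | 28.5%, 42, 97% | 5.7%, 56, 92% | 2.8%, 57, 92% |
| 3.5 | 17.1%, 49, 95% | 1.6%, 58, 91% | 6.2%, 55, 92% |
| 3 | 9.0%, 54, 93% | 0.1%, 59, 91% | 10.7%, 53, 94% |
| 2.5 | 3.7%, 57, 92% | 0.6%, 59, 91% | 15.9%, 50, 95% |

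The gain vanishes where b is near 1 (s0 = 3, ρ = 0.5: b = 0.5 × 5.77/3 = 0.96). The first row requires a baseline SD of 5/√(2(1 − ρ)) = 4.23, 5.00 or 6.45. If the PSQI maximum is 21 (an assumption; the documents do not give it), a flat spread over 10 to 21 has SD 3.45 and no distribution there exceeds 5.5. The 6.45 case is then impossible. A baseline SD above the Day 30 SD would give larger gains, but I leave it out because the entry floor narrows baseline scores.

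**Step 3: error rates.** An illustrative null simulation used 4 sites × 2 PSQI strata, blocks of 2/4/6, 60 per arm, 6,000 runs, baseline about 15 with SD 3.5 before truncation to 10–21, slope 0.6 and residual SD 4. Two-sided rejection rates at 5% were 4.3% for the t-test on change, 4.9% for the adjusted model, and 5.8% for the best of t-test, Mann-Whitney and adjusted model. The simulation standard error is √(0.05 × 0.95/6000) = 0.28 points. A one-sided version added an average of Days 14 and 30 as a fourth option (assumed ρ 0.3–0.5, baseline SD 3–5, follow-up SD 4.5–5). Each test alone rejected in about 2.2 to 2.8% of runs, and the most favourable of the four in 4.1 to 4.9%. These are worst cases, in which the best result is always taken.

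**Step 4: strata.** 4 named sites × 2 PSQI levels = 8, against the four stated in section 7.1.

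**The case against.** Several points on the other side stand.

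- The t-test is valid under stratified randomisation, and its 90% power reproduces. A reader might infer that the primary analysis is biased or underpowered; nothing in the documents supports that.
- A reader might take a fixed saving, such as 15 to 35% of the variance, from the equal-SD formula. The documents give none of its inputs, and the low end needs a baseline SD of 6.45, which is implausible with entry at PSQI 10 or more.
- A reader might infer that the primary p-value could come from any test in section 7.2. The transformation and Mann-Whitney wording is a general rule beside the text on patient characteristics, and it recurs for secondary outcomes in section 7.6. Only the repeated-measures sentence names the PSQI change.
- A repeated-measures ANOVA on just Day 0 and Day 30 has a group-by-time test identical to the equal-variance t-test on change, so on that reading there is no conflict. But neither time points nor model are specified, and PSQI is also collected at Day 14.
- The p ≤ 0.25 rule and the optional stepwise step sit under secondary outcomes and cannot alter the primary p-value.
- Site terms could be sparse at the first interim look, with 20 per arm and an open number of sites. The model needs a pooling rule.

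**Conclusion.** The point holds in two parts. First, omitting baseline PSQI and site from the primary test gives up precision. For ρ of 0.3 to 0.7 and a baseline SD no larger than the Day 30 SD, the loss is roughly 0 to 35% of the change-score variance. The 35% applies only at ρ = 0.3 with equal SDs; for some smaller baseline SDs the loss is near zero. By noncentral t, power at 60 per arm is 90.3% unadjusted and at most 98.1% adjusted. This is a missed gain, not an error in the sample size or in validity.

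Second, and more important, section 7.2 gives the primary endpoint both a named test and an unspecified one, and the SAP does not settle it. The claimed 2.5% one-sided rate depends on the test being fixed beforehand. The simulated inflation is modest under two-sided testing (5.8% against 5%) and reaches about 4 to 5% against 2.5% one-sided if the most favourable of four analyses is always reported.

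The secondary covariate rule and the strata count are lesser, related corrections.

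**What to change.** In both the protocol and the SAP:

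1. Name one primary analysis: a linear model of Day 30 PSQI on treatment, continuous baseline PSQI and site, reporting the adjusted difference with 95% CI. Pool small sites by a rule set in advance. Use the same model at both interim looks.
2. Label the t-test/Welch test and any repeated-measures analysis as sensitivity analyses. Delete the sentence leaving the test of the PSQI change to later judgement. State that the general transformation and Mann-Whitney rule does not apply to the primary endpoint.
3. For each secondary scale, replace the p ≤ 0.25 and stepwise selection with that scale's own baseline, site and PSQI stratum.
4. Correct the strata count in section 7.1 to agree with Table #2 (at least eight).

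The cost is wording and an amendment through the IRB. Site and the baseline scales are already collected. The change should be dated and made without sight of unblinded outcome data. The objectives table in section 3 mentions interim and secondary analyses of current data without saying whose; if they are this trial's, the amendment should say so and justify the timing.
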